## **X. PROTECTION AGAINST RISKS:**

This is a multicenter study. All identifying data will be stored at the University of Washington or Fred Hutchinson Cancer Research Center using standard security techniques. Hard copies of data collection materials that have identifiers will be locked in the office of the study PIs or a room with limited access by specific individuals. When possible, redacted (de-identified) versions of the data will be used for coding and data analysis. Personal identifiers will be stored in the database on OneDrive, which is HIPAA-compliant, password protected, and only accessible to specific individuals. Transfer or storage on portable devices (e.g., laptops, flash drives) will be encrypted. The devices on which this information is stored will be accessible only to individuals who need access to the data.

To reduce distress, study participants will be given the opportunity to skip any questions that they are not comfortable answering. Additionally, all participants will be reminded that participating in research is always optional, and they may terminate their participation at any time without consequences. All members of the research team will be required to complete Protecting Human Research Participants training offered before enrollment of participants begins. Only those research team members with login credentials and passwords will be granted access to the centralized data capture system, where data are stored and audited. As previously stated, to mask participant identity, participants will be assigned unique study identifiers (participant ID numbers) at the time of enrollment. Only specific members of the study team will be able to link the participant ID to the participant’s name. As all survey data collected will be via parent report only, there are no concerns in this study about the confidentiality of the youth’s answers from the parent. Individual subject level data collected from the secondary outcomes surveys will not be shared with the schools in order to protect the privacy of participating youth; school and study level summary reports from the secondary outcome surveys will be shared with participating schools, but in order to protect youth confidentiality, no summary tables will include cell sizes smaller than five.

## **XI. STATISTICAL ANALYSES**

The primary analysis will be based on the average number of onsite learning hours per week over the study period for each student. The data will be analyzed using a linear mixed effects model with district and randomization arm as fixed effects, and school and classroom within school as random effects. We will first test for any difference between the randomization arms using  $\alpha = 0.05$  and report the comparisons between arms.

## **XII. ADVERSE EVENT REPORTING**

**Serious Adverse Events:** Serious adverse events (SAEs) under Good Clinical Practice (GCP) guidelines include death, a life-threatening reaction to a study procedure, hospitalization, or

significant or persistent disability or impairment. Other events may also be considered a serious adverse event if, based on medical judgement, the event jeopardized the patient to the point of requiring medical or surgical intervention.

**Other Adverse Events:** This will include any untoward medical event that occurs in a participant, any unfavorable sign or symptom disease temporally associated with the study, or any noxious or unintended response to the study procedures. These other adverse events can be anticipated based on what we know about reactions to study procedures, or unanticipated.

Unanticipated adverse events are those that are either unexpected in terms of nature, severity, or frequency, especially if they indicate that there is greater risk of harm than previously recognized.

Participants will be instructed to report any adverse events related to the study procedures to research staff by phone call or email. Emails received by study staff indicating that an adverse event has occurred in a household will be followed up by a phone call to that participant. All adverse events will be reported using an official Adverse Event Report Form to the designated principal investigator ([name]) or designee for review within 48 hours. The review will determine if there is any indication of the event being related to study procedures. If this review determines the event to be both anticipated and related to the study, it will be logged in the centralized data capture system. If the review determines the event to be unanticipated and related to the study, a report of the event will be submitted to the UW IRB.

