### **Aim 2**

Prior to randomization, the participant or participants' (for families enrolling more than one child) parent/legal guardian will complete a baseline questionnaire with demographic and COVID-19 mitigation behavior questions after providing informed consent/assent. Randomization will be conducted at the school-level. Participants in the intervention group will receive risk communication materials in the form of: (1) 3 comic books with accompanying read-along videos for children and (2) 2 videos for parents, once a month for three consecutive months. Participants randomized to the comparison group will be provided the same risk communication materials at the end of the school year as a delayed intervention. Parents of participants randomized to the Intervention group will be given two videos focused on COVID-19 topics such as testing and

vaccination throughout the school year. Similarly parents of participants randomized into the comparison group will receive the two videos as a delayed intervention. Throughout the duration of the study, participants will receive weekly brief email or text message reminders to complete an online Weekly Check-in Survey that collects information about COVID-19 symptoms, school absenteeism, and SARS-CoV-2 exposure. Parents of students who report that their child is experiencing COVID-19 symptoms will then be prompted to answer more questions about the illness, and any healthcare that they may have received. At Post Survey 1 and Post Survey 2 assessments, parents will be asked to complete a short online survey to update their demographic information, child's COVID-19 vaccination status, and the child's SARS-CoV-2 mitigation behaviors.

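### The adverse event section defines events without regard to cause but asks families only for related ones, and logs only related events that were anticipated, so the harms log will be incomplete.

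*Protocol*

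**What the plan says.** Protocol XII (Adverse Event Reporting) has three parts.

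- **Definitions.** For the serious class: "Serious adverse events (SAEs) under Good Clinical Practice (GCP) guidelines include death, a life-threatening reaction to a study procedure, hospitalization", followed by lasting disability and, on medical judgement, events needing intervention. For other events: "This will include any untoward medical event that occurs in a participant", together with signs that merely coincide in time with the study and unintended responses to its procedures. Death, hospitalisation and untoward medical events carry no relatedness condition.
- **Collection.** "Participants will be instructed to report any adverse events related to the study procedures to research staff by phone call or email". An email that mentions an event is followed by a phone call.
- **Handling.** "All adverse events will be reported using an official Adverse Event Report Form to the designated principal investigator" "or designee for review within 48 hours". The review decides whether the event may be related to study procedures. If it is "both anticipated and related to the study, it will be logged in the centralized data capture system". If it is unanticipated and related, a report goes to the IRB. No other outcome is described.

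Elsewhere, Protocol III (Aim 2) has a weekly check-in in which parents reporting COVID-19 symptoms in their child are "prompted to answer more questions about the illness, and any healthcare that they may have received". The Data and safety monitoring plan provides for no independent committee and calls the study minimal risk. The SAP contains no adverse event summary or analysis.

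**The concern.** The definitions and the collection rule have different scope. Relatedness is properly a finding of the review, yet here it is also the entry condition, applied by a parent. In this trial that judgement is hard for a family to make. The materials aim to change testing and vaccination behaviour, and Protocol VIII offers a gift card to encourage travel to the district testing site, while the testing itself is declared outside the study's scope. A parent may reasonably not see an event that follows an encouraged behaviour as related to a study procedure.

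The logging rule then runs opposite to what one would expect. The related events that nobody foresaw, which Section XII itself links to a risk greater than previously recognised, are the ones with no stated log entry. The serious class is defined in detail but has no function.

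At stake is whether the study's harms record is complete and can be relied on if anyone asks what happened to the enrolled children.

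**Working it through.** No sample size, power or error rate depends on this, so there is nothing to recompute. The check traces an event through Section XII and then looks for another route in either document.

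**Step 1: does the event reach staff?** The definitions cover untoward medical events in general. The request to families covers only those related to study procedures. An event that the family thinks unrelated is inside the definition and outside the request.

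**Step 2: what happens once staff know?** Every adverse event goes on a report form and is reviewed within 48 hours. This step has no relatedness filter and no separate timeline for serious events.

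**Step 3: what follows the review?** Relatedness and anticipation give four combinations:

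| Review finding | Central log | IRB report |
|---|---|---|
| Related, anticipated | yes | not stated |
| Related, unanticipated | not stated | yes |
| Unrelated, anticipated | not stated | not stated |
| Unrelated, unanticipated | not stated | not stated |

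One of the four is logged and one is sent to the IRB. The table reads the same for serious and non-serious events, because no step refers to seriousness. The anticipated/unanticipated distinction is itself introduced under other adverse events, so how it applies to serious ones is not clearly stated.

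**Step 4: is there another route?**

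- The weekly check-in (Protocol III, Aim 2; Protocol V, Aim 2 Study Procedures) asks about COVID-19-type symptoms, care sought, absence and exposure. The further illness questions open only when symptoms are reported. No general question on hospitalisation or death is described, and no text links an answer to the report form.
- Follow-up of non-responders (Protocol V, Follow-up Behavior Update Surveys) includes queries to the district and home visits. Staff might learn of an event this way, but the text does not treat it as an adverse event source.
- Data-quality checks (Protocol IX) look for missing, inconsistent or out-of-range entries.
- SAP 12.c marks missing post-survey responses as loss to follow-up.

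**Result.** A hospital stay without COVID-19 symptoms that the family thinks unrelated is requested by no rule or survey described; at most an absence is recorded. A death that is not volunteered may show only as non-response. If staff do hear of either, a form and a review exist, but a finding of unrelated leads to no stated log entry or IRB report.

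**The case against.** The intervention is comic books and videos. The only risk that Protocol VII names is a breach of confidentiality, and testing is run by the district. Collecting mainly related events can be a proportionate choice in such a study, and unrelated paediatric admissions would say little about harm from the materials. A broad definition with narrower solicitation could be called a mismatch to tidy up. This stands as a limit on the weight of the point. It does not make the section consistent: a deliberate restriction would be stated as one, and the serious class would be either used or dropped.

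Some stronger readings are tempting, but the documents do not support them.

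- *Unrelated events leave no record at all.* Any adverse event that reaches staff goes on a report form and is reviewed. For those events the gap is the missing log or IRB step. A stay entered in the check-in, or an absence in district data, is also a study record, though not an adverse event record.
- *Serious related events escape oversight.* In an educational trial a related death or hospitalisation would almost always be unanticipated, and unanticipated related events go to the IRB. What is missing is the log entry.
- *Hospital stays given in the weekly survey would never be reviewed.* The survey is not shown to capture hospital stays, and the duty to put all adverse events on a form is not limited to phone and email. The supportable statement is that no survey trigger is written down.
- *A serious-event comparison by arm would be wrong.* No such comparison is planned.

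**Conclusion.** The point holds as an inconsistency within Protocol XII. The family screens on causality ahead of the review meant to decide it. Of the four possible review findings, only anticipated related events have a stated log entry, and seriousness alters no step. A death or hospitalisation that the family thinks unrelated may leave no adverse event record, and the central log would omit the unanticipated related events.

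The size is modest. No event rate is given, so the number of events missed among the 900 planned children cannot be estimated, and no efficacy figure is touched. The conclusion assumes that Section XII is followed as written and that no separate manual or instrument adds an intake or logging step that these documents do not show. The section should be changed because the correction is cheap and improves safety ascertainment.

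**What to change.** Reconcile the definitions, reporting instruction and outcomes in Protocol XII:

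1. Ask families to report any event that meets the protocol's own serious definition, whether or not they think the study caused it. Keep the relatedness filter for non-serious events, so that routine colds stay outside.
2. Log every reviewed serious event and every related event, anticipated or not, with seriousness, relatedness and arm. Keep the existing IRB step for unanticipated related events.
3. State that an event meeting the serious definition that staff learn of from any source, including check-in answers and follow-up contact, enters the existing report-form review.

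This uses the form, the 48-hour review and the data system already in place. The cost is a few sentences of protocol text, the added log fields and a little coordinator time on serious events that prove unrelated.

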### **XIII. END OF STUDY**

The end of the study is defined as when the last participant has had their last data collected at the end of the study period. Overall, the study is projected to last until June 2023 when the school year ends, and the overall study is projected to end between April to June 2024, if funding allows.

### **XIV. DEFINITIONS**

**Acute Respiratory Illness (ARI):** We will use the CDC definition of ARI that includes disease that typically involves the airways within the nose and throat and may or may not include fever. ARI is generally defined by the presence of two or more symptoms such as fever, cough, runny nose or nasal congestion, or sore throat. ARI is more sensitive (broader) than influenza-like illness to describe illness consistent with influenza because fever/feverishness is not required.

**Exposure/Close contact:** Per CDC definition, a close contact is someone who was less than 6 feet away from infected person (laboratory-confirmed or a clinical diagnosis) for a cumulative total of 15 minutes or more over a 24-hour period (for example, *three individual 5-minute exposures for a total of 15 minutes*).

- **Exception:** In the **K-12 indoor classroom** setting or a structured outdoor setting where mask use can be observed (i.e., holding class outdoors with educator supervision), the close contact definition excludes students who were between 3 to 6 feet of an infected student (laboratory-confirmed or a clinical diagnosis) if both the infected student and the exposed student(s) correctly and consistently wore well-fitting masks the entire time.

**Laboratory Confirmed COVID-19 Infection:** an individual who tests positive for SARS-CoV-2 via an approved rapid antigen or PCR test.

**Absenteeism:** total number of school days missed by each individual student participant, both for the entire year and month-by-month, as captured and shared with us by school district administrative data systems.

**Emotion Regulation:** these can also be referred to as “internalizing symptoms”, or as depressive and anxiety symptoms.

## 2. Study Schema and objectives

[figure not shown]
Purpose:	To determine the effectiveness of risk communication for parents and students on students' attendance to school, COVID-19 testing and vaccine uptake
Design:	A clustered randomized controlled trial of risk communication intervention
Central Hypotheses:	Our central hypotheses are that students and parents who view the risk communications will be more likely to have less school absence, increased covid-19 testing and vaccine uptake.
Primary Objectives:	

• To determine if implementing three COVID-19 education comic books for children and two COVID-19 education videos for parents will lower school absenteeism, increase COVID-19 testing, and vaccine uptake in children.

Secondary Objectives:	

• To determine if implementing three COVID-19 education comics books for children and two COVID-19 education videos for parents will increase physical activity, improve sleep, increase emotional regulation in children.

• To determine if implementing three COVID-19 education comics books for children and two COVID-19 education videos for parents will increase physical activity, improve sleep, decrease depression and anxiety in parents

Population:	Children ages 5-13 enrolled in kindergarten to 5 th grade in Yakima School District
Study Size:	14 schools randomized; 7 to intervention and 7 to comparison arms with 450 children in each arm; a total of 900 children from 14 schools.
Primary Outcome Measurements:	

A. Attendance captured through the school district

B. COVID-19 testing data available through the school district testing program and self-reported survey

C. COVID-19 vaccine data available through self-reported survey

Study Duration:	2 years including enrollment period, 2 months to deliver the intervention, 5 months for post 1 survey, 7 months weeks for post 2 survey.

## 3. Study Design

ROSSEY study is a cluster randomized controlled trial to test COVID-19 risk communication intervention with 900 participants from 14 elementary schools in the Yakima School District during

the 2022-2023 school year. Schools are randomized 1:1 (matched by school size and English language learners) to either intervention or control group. Students and parents randomized to the intervention group receive the COVID-19 risk communication intervention. Students and parents randomized to the control group receive the same risk communication intervention at the end of the study as a delayed intervention.

### Study Timeline

## 4. Sample size and power

**For month 5 outcome.** We will enroll 900 elementary school students from 14 schools in the Yakima School District during the 2022-2023 school year. The sample size of 7 schools per study arm and an average of 50 students per school will provide 90% power to detect a difference of at least 4 hours per week ( $SD=8.0$ ) of in-person school attendance between the intervention and control groups, while assuming intra-cluster correlation (ICC) of 0.05 and type I error rate of 0.05. The estimated sample size of 14 schools with 900 students provides 80% power to detect a difference of 20% or more in COVID-19 vaccination rates between the two study arms, assuming ICC of 0.05 and type I error rate of 0.05.

Minimum detectable difference in hours per week between intervention arms in proposed cluster RCT assuming enrollment of 15 students per classroom, 80% power and two-sided type I error rate of 0.05.					
		Two Arm			
	Number of clusters per arm	30		40	
	ICC	.01	.10	.01	.10
Standard Deviation	5.0	1.0	1.5	.87	1.3
	7.5	1.5	2.2	1.3	1.9

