### **Sample Size**

We plan to enroll at least 900 elementary students from 14 schools in the the Yakima School District during the 2022-2023 school year into the research study. This will give us at least 80% power to detect a difference of at least 4 hours per week of in-person school attendance between the intervention and control arms.

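### SAP section 4 rests its attendance power on 50 students per school (700 in all) but enrols 900 and rests its vaccination power on 900, without explaining the difference

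*SAP*

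**What the plan says.** SAP section 4 gives the size three times in one paragraph. It opens with "We will enroll 900 elementary school students from 14 schools in the Yakima School District". It then supports the attendance outcome with "The sample size of 7 schools per study arm and an average of 50 students per school will provide 90% power". The effect behind that figure is 4 hours of attendance per week with an SD of 8.0, and the assumptions are an ICC of 0.05 and a type I error of 0.05. It closes on vaccination with "The estimated sample size of 14 schools with 900 students provides 80% power" for a 20% difference, at the same ICC and error rate.

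Elsewhere the size is always 900. SAP section 2 has "7 to intervention and 7 to comparison arms with 450 children in each arm; a total of 900 children from 14 schools", SAP sections 3 and 5 repeat 900, and the Protocol under Sample Size has "We plan to enroll at least 900 elementary students from 14 schools". The Protocol claims at least 80% power for the same 4-hour difference.

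SAP section 4 states no vaccination base rate, power method, spread of school sizes or allowance for loss.

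**The concern.** An average of 50 students in 14 schools cannot describe a trial of 900 in 14 schools. The two power statements sit next to each other and concern two of the three co-primary outcomes (SAP section 7a), yet they use different numbers of students per school.

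If 50 is a leftover or mistaken figure, the attendance power was worked out for a smaller trial than the one planned. If 50 is the number expected to be analysed after losses, the vaccination power was worked out for a larger one, and the 80% might not be reached. The reader is not told which applies.

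**Working it through.** **Sizes.** 7 × 2 × 50 = 700. 900 / 14 = 64.3, and 450 / 7 = 64.3. The gap is 200 students, or 200 / 900 = 22%.

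**Inputs from SAP section 4.** 7 schools per arm; difference 4 h per week; SD 8.0; ICC 0.05; type I error 0.05; vaccination difference 20%.

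**Assumptions.** Two-sided test (stated only in the caption of the section 4 table); the 20% is absolute; equal school sizes; school-level comparison by t with 2 × (7 − 1) = 12 degrees of freedom; vaccination base rates of 20–60%, since none is given.

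**Formulas.** With m students per school, design effect DE = 1 + (m − 1) × 0.05 and effective size per arm n = 7m / DE. Power comes from the non-central t with non-centrality equal to difference / SE. For attendance, SE = 8 × √(2 / n). For vaccination, SE = √{[p₁(1 − p₁) + p₂(1 − p₂)] / n}.

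**Attendance**

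| m | DE | n per arm | SE (h) | 4 / SE | Power |
|---|---|---|---|---|---|
| 50 | 3.45 | 101.4 | 1.123 | 3.56 | 90.4% |
| 64.3 | 4.16 | 108.1 | 1.088 | 3.68 | 92.1% |

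The stated 90% is reproduced at 50 per school. Moving to 64.3 adds about 1.7 points.

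**Vaccination, 20-point difference**

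| Rates compared | Power, m = 50 | Power, m = 64.3 |
|---|---|---|
| 20 vs 40%, or 60 vs 80% | 83.2% | 85.4% |
| 25 vs 45%, or 55 vs 75% | 80.0% | 82.4% |
| 30 vs 50%, or 50 vs 70% | 77.8% | 80.3% |
| 40 vs 60% | 76.1% | 78.7% |

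The stated 80% can be reproduced at either size, depending on the base rate. Moving from 50 to 64.3 adds 2 to 3 points.

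**Sensitivity to method**

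- Normal approximation: attendance 94.5% at 50 and 95.7% at 64.3. Vaccination at 50 per school is lowest at 40 vs 60%, with 81.8% (pooled null variance) or 82.8% (unpooled).
- School sizes varying with a coefficient of variation of 0.3 (assumed), m = 64.3: DE = 1 + (1.09 × 64.3 − 1) × 0.05 = 4.45, SE = 1.126, attendance power 90.3% (t, 12 df).
- 6 degrees of freedom, for the matched pairs in the Protocol's randomization plan: attendance 84.1% at 50 and 86.2% at 64.3.

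**The case against.** A reader might infer that the two stated powers must come from two different designs, with 90% attainable only at 50 per school and 80% only at about 64. The documents do not support that. At 50 per school with 25 vs 45% or 55 vs 75% vaccinated, one trial gives 90.4% for attendance and 80.0% for vaccination. At 64.3 per school, modest variation in school size brings attendance power to 90.3%. With no base rate, method or size variation stated, none of this can be excluded.

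It is also tempting to say that the planned size is unclear, or that vaccination is underpowered at 50 per school. The target is clear: 900 appears throughout, and 700 is never stated. The vaccination shortfall depends on the method, because under a normal approximation power at 50 per school stays above 80% at every base rate examined. If 900 is the size used, the stated 90% for attendance is slightly conservative. The Protocol's claim of at least 80% is met at either size in the 12-df calculation.

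The best explanation for the 50 would be an attrition allowance of about 22%. The SAP does not state one, and it would be applied the wrong way round. Attendance comes from district records, where loss should be small, yet it gets the smaller number. Vaccination comes from parent surveys, where loss is more likely, yet it gets the full 900.

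These objections limit what can be concluded from the powers. They leave the unexplained gap between 700 and 900 standing.

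**Conclusion.** The point holds as an internal inconsistency in SAP section 4. An average of 50 per school is incompatible with 900 students in 14 schools, and nothing in the documents reconciles them. That part is simple arithmetic and does not depend on a power method.

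The consequence is small, because the fixed number of 14 schools limits what extra students per school can add: about 1.7 points for attendance and 2 to 3 points for vaccination. Those figures rest on equal school sizes, 12 degrees of freedom, a two-sided test and assumed base rates. The inconsistency does not show that the trial is underpowered for attendance, and it gives no reason to change the enrolment target.

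**What to change.** In SAP section 4, put both powers on one stated number of students per school:

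- If 900 is the size analysed, replace the average of 50 with about 64 (450 per arm over 7 schools) and restate attendance power at that size, about 92% under the assumptions above.
- If 50 is the number expected to be analysed per school after losses, say so, give the loss assumed, and recompute vaccination power on the same 50, about 76–83% under the assumptions above.

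In either case state the vaccination base rate and the power method, including the degrees of freedom and any allowance for unequal school sizes. The final figures should come from the sponsor's own method and inputs, since those here rest on assumptions. Keep 900 as the enrolment target in both documents.

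The cost is a few sentences in one SAP section, and possibly a slightly less favourable vaccination power. No extra enrolment is needed, and the design and analysis do not change.
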